#### **8.2.1.3. Primary Analysis**

The study primary analysis will be conducted when all enrolled subjects have discontinued the study or have been on treatment of GS-4224 for at least 48 weeks and completed response assessment of Week 48.

Prior to the final analysis, interim analyses may be conducted, and the analyses may be submitted to regulatory agencies to seek guidance for the overall clinical development program.

### **8.2.2. Final Analysis**

The final analysis will be performed after all subjects have completed or discontinued from the study, outstanding data queries have been resolved or adjudicated as unresolvable, and the data have been cleaned and finalized.

## **8.3. Analysis Conventions**

### **8.3.1. Analysis Sets**

#### **8.3.1.1. All Enrolled Analysis Set**

The All Enrolled Analysis Set includes all subjects who received a study subject identification number in the study after screening. This will be the primary analysis set for analyses of subject characteristics.

#### 8.3.1.2. Full Analysis Set

The Full Analysis Set (FAS) includes all subjects who took at least 1 dose of study treatment. It will be used in the analyses of efficacy endpoints.

#### 8.3.1.3. Safety Analysis Set

The Safety Analysis Set includes all subjects who enrolled to the study and receive at least 1 dose of study treatment, with treatment assignments designated according to the actual treatment received. This analysis set will be used in the analyses of safety variables as well as study treatment administration.

#### 8.3.1.4. DLT-Evaluable Analysis Set

The DLT-Evaluable Analysis Set includes all subjects in the Safety Analysis Set who enroll to the dose escalation cohorts (up to the first 6 subjects in the 1000 mg BID dose escalation cohort; CCI [REDACTED]), complete  $\geq 75\%$  of the prescribed study treatment and have safety assessments through the protocol-specified DLT assessment window (first 21 days of study dosing, inclusive) or have experienced a DLT prior to the completion of first 21 days of study dosing. Safety assessment relevant to the DLT-Evaluable Analysis Set definition will include laboratory serum chemistry tests and hematology tests as specified in the protocol. Determination of the MTD will be based on the DLT-Evaluable Analysis Set.

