**Statistical Methods:**

The study primary analysis will be conducted when all enrolled subjects have discontinued the study or have been on treatment of GS-4224 for at least 48 weeks and completed response assessment of Week 48.

Analysis Data Set

The All Enrolled Analysis Set includes all subjects who received a study subject identification number in the study after screening.

The Full Analysis Set (FAS) includes all subjects who took at least 1 dose of study treatment. It will be used in the analyses of efficacy endpoints.

The Safety Analysis Set will include data from all subjects who receive at least 1 dose of study treatment, with treatment assignments designated according to the actual treatment received. This analysis set will be used in the analyses of safety variables as well as study treatment administration.

The DLT-Evaluable Analysis Set includes all subjects in the Safety Analysis Set who enroll to the dose escalation cohorts (up to the first 6 subjects in the 1000 mg BID dose escalation cohort; excluding the Dose Escalation Biopsy Substudy), complete  $\geq 75\%$  of the prescribed study treatment and have safety assessments through the protocol-specified DLT assessment window (first 21 days of study dosing, inclusive) or have experienced a DLT prior to the completion of first 21 days of study dosing. Safety assessment relevant to the DLT-Evaluable Analysis Set definition will include laboratory serum chemistry tests and hematology tests as specified in the protocol. Determination of the MTD will be based on the DLT-Evaluable Analysis Set.

The PK Analysis Set will include data from subjects in the Safety Analysis Set who have received the study drug and have at least 1 sample with detectable drug concentration.

An IRC may review radiographic data in order to provide independent evaluation of tumor status. Tumor response status and progression will be assessed by the IRC using RECIST v1.1 with modifications or Lugano 2014 response criteria for cHL.

Efficacy Analysis

In efficacy analysis, ORR will be evaluated by tumor type and treatment in FAS. Tumor types with less than 5 subjects enrolled will be pooled for ORR summary. Subjects who do not have sufficient baseline or on-study tumor assessment to characterize response will be counted as nonresponders. Estimates and the corresponding 95% CIs based on the Clopper-Pearson exact method will be provided.

---

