**Table 3-1. Dose Escalation (Phase 1b) Dose Levels**

Dose Level Schema	
GS-4224 (mg)	Fold Increase
400 QD	-
700 QD	≤ 3×
1000 QD	≤ 3×
1500 QD	≤ 3×
1000 BID	≤ 3×

In the 1000 mg BID dose cohort, at least 6 (as part of the initial 3+3 design) and up to an additional 14 subjects (for a total of 20 subjects) with locally advanced, inoperable or metastatic cancer expressing PD-L1 (tumor proportion score [TPS] ≥ 10% or combined positive score [CPS] ≥ 10) and who have not previously been treated with anti-PD-1/L1 antibodies will be enrolled. The additional 14 subjects will not be enrolled at the 1000 mg BID dose level if the subject incidence of DLTs is > 1 in the first 6 subjects. If the subject incidence of DLTs is > 1 in the first 6 subjects at 1000 mg BID, then 20 additional subjects with locally advanced, inoperable or metastatic cancer expressing PD-L1 [TPS ≥ 10% or CPS ≥ 10] and who have not previously been treated with anti-PD-1/L1 antibodies will enroll at the MTD. Tumor types of interest include non-small cell lung cancer (NSCLC), melanoma, renal cell carcinoma (RCC), urothelial, esophageal, hepatocellular carcinoma (HCC), cutaneous squamous cell, Merkel cell, MSI-H cancers, and cHL. See [Appendix 3](#) for the PD-L1 expression requirement for specific tumor types.

For the 1000 mg BID dose cohort, subjects must have available sufficient and adequate formalin-fixed tumor tissue sample preferably from a biopsy of a tumor lesion obtained either at the time of or after the diagnosis of advanced disease has been made and from a site not previously irradiated. Alternatively, subjects must agree to have a biopsy taken prior to entering the study to provide adequate tissue. Subjects with melanoma, Merkel cell, MSI-H cancers, and cHL are not required to have archival or fresh biopsy tissue.

The safety and tolerability of each dose level will be assessed by a safety review team (SRT) after up to 6 subjects enrolled in the dose level have been followed for at least 21 days after the first dose of GS-4224 or 2 DLTs have been observed, whichever is earlier. See Section 3.2.3 for more information about the SRT.

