The initial block of each dose consists of 3 subjects. Dose escalation may occur if no subjects experience DLTs during the first 21 days of study drug dosing. If 1 subject within the initial cohort of 3 subjects experiences a DLT during the first 21 days of study drug dosing, an additional 3 subjects will be enrolled at the same dose level. If no DLTs are observed in the additional 3 subjects, dose escalation will occur. If 2 or more of the 6 subjects experience DLTs within the first 21 days, dose de-escalation to an intermediate dose will occur. The MTD is the

highest dose level with a subject incidence of DLTs during the first 21 days of study drug dosing of 0 or 1 out of 6. A minimum of 6 subjects need to be treated at a dose level before this dose level can be deemed as the MTD. A subject who is withdrawn from the study before the completion of the first 21 days for a reason other than a DLT will be replaced.

If 2 or more delayed DLT-type AEs are noted after the first 21-day observation period within a dose escalation cohort, further accrual at all sites will be held pending safety analysis of the event, and will be restarted only with investigator and sponsor approval.

The SRT will review safety and relevant clinical data and make the dose escalation/stay/de-escalation decision. Source Data Verification (SDV) is not required to be performed prior to SRT meetings, as there will be alternative quality control checks implemented. These checks will be described in the SRT Charter.

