#### 4.1.2. Subject Replacement

A subject who is withdrawn from the study before the completion of the first 21 days for a reason other than a DLT or who receives less than 16 of 21 doses of GS-4224 in the first 21 days will be replaced.

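### The DLT-Evaluable set used for the MTD has a six-subject limit at 1000 mg BID only, makes no provision for replacements, and has no limit in the SAP, so its denominator need not match the 0-or-1-of-6 rule

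*Protocol*

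**What the plan says.** **The set.** Protocol Section 8.3.1.4 starts from treated subjects in the dose escalation cohorts and attaches a limit to that enrolment condition: "up to the first 6 subjects in the 1000 mg BID dose escalation cohort". It then requires at least 75% of prescribed treatment and safety assessments through Day 21, "or have experienced a DLT prior to the completion of first 21 days of study dosing". It closes: "Determination of the MTD will be based on the DLT-Evaluable Analysis Set". Part of the parenthesis is redacted there. The same definition is legible in the synopsis under Statistical Methods, where the only other carve-out is "excluding the Dose Escalation Biopsy Substudy".

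**Replacement.** Section 4.1.2 covers "A subject who is withdrawn from the study before the completion of the first 21 days for a reason other than a DLT" and anyone with fewer than 16 of 21 doses, and says such subjects are replaced. Section 3.2.1 repeats the withdrawal part. Neither exempts 1000 mg BID.

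**The two branches.** Section 3.2.1 plans at least six subjects at 1000 mg BID for the 3+3 step and up to 14 more if that step shows no more than one subject with a DLT. If more than one of the first six has a DLT, "then 20 additional subjects with locally advanced, inoperable or metastatic cancer expressing PD-L1" enrol at the MTD instead.

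**The MTD rule.** The MTD is the highest level with a DLT in none or one of six subjects, and "A minimum of 6 subjects need to be treated at a dose level before this dose level can be deemed as the MTD". No rule is given for a larger denominator.

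**The SAP.** Section 3.1.4 defines the same set with the biopsy exclusion but without the six-subject limit. Section 7.1.7 summarises DLTs on this set and keeps the label DLT-type AE for events after Day 21. Section 7.7 reports no deviations from the protocol's safety analyses.

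**The concern.** DLT incidence is the primary endpoint, and the set that supplies its denominator also fixes the MTD. Three stated rules pull that denominator away from six:

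- at 1000 mg BID, a limit that sits before the evaluability test and does not mention replacements;
- at the MTD in the other branch, no limit on a group of 20 recruited for the same purpose as the 14 who are excluded at 1000 mg BID;
- in the SAP, no limit at all.

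Two programmers working faithfully from the two documents could report different DLT incidences at 1000 mg BID. A reader could also find an MTD supported by five subjects, or by more than 20, under a rule written for six. Copying the protocol's limit into the SAP would align the documents but leave the first two points open.

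**Working it through.** **Planned size.** The documents state up to 44 subjects for Phase 1b and show no derivation. The natural count is four once-daily levels × 6 + 20 at 1000 mg BID = 44, which agrees. If all four once-daily levels reach six and the other branch is taken, the count is 4 × 6 + 6 + 20 = 50.

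**Possible size of the set at the level concerned**

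| Situation | Source | Evaluable subjects in the set |
|---|---|---|
| 1000 mg BID, limit read literally, one of the first six non-evaluable | Protocol 8.3.1.4 | 5 |
| 1000 mg BID, replacement takes the vacated place | Protocol 8.3.1.4 read with 4.1.2 | 6 |
| 1000 mg BID | SAP 3.1.4 | up to 20 |
| MTD level after 1000 mg BID is not tolerated | Protocol 8.3.1.4 with 3.2.1 | up to 6 + 20 = 26 |

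**How often a replacement is needed.** The documents give no non-evaluable rate q, so I assume 5%, 10% and 20%. The chance that at least one of the first six is non-evaluable is 1 − (1 − q)^6:

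- q = 0.05: 1 − 0.95^6 = 0.265
- q = 0.10: 1 − 0.90^6 = 0.469
- q = 0.20: 1 − 0.80^6 = 0.738

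These are chances that the question arises, not error rates. The set falls short only under the literal reading.

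**What five instead of six does to the rule.** The binomial chance of 0 or 1 DLT is:

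| True DLT rate | 5 evaluable | 6 evaluable |
|---|---|---|
| 10% | 0.919 | 0.886 |
| 20% | 0.737 | 0.655 |
| 30% | 0.528 | 0.420 |

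**How many of the 20 would enter.** The evaluability condition still applies. At q = 5%, 10% and 20%, 20(1 − q) = 19, 18 and 16 are expected to be evaluable. The chance that all 20 are, (1 − q)^20, is 36%, 12% and 1%. So 26 is a maximum.

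**Carrying the MTD rule to 26.** Let X be the subjects with a DLT among the first 6, Y among the added 20, and p the true DLT rate (assumed). Condition on X ≤ 1, since the level was chosen as the MTD.

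- Count reading (limit stays at 1 DLT): P(X + Y ≥ 2 | X ≤ 1) = 1 − P(X + Y ≤ 1) / P(X ≤ 1).
- Rate reading (limit is 1/6, and 26/6 = 4.33, so at most 4 DLTs): [P(X = 0)·P(Y ≥ 5) + P(X = 1)·P(Y ≥ 4)] / P(X ≤ 1).

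| p | Count reading | Rate reading |
|---|---|---|
| 5% | 35% | 0.6% |
| 10% | 72% | 8% |
| 15% | 89% | 26% |

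For example, at p = 5% the count reading is 1 − 0.624/0.967 = 0.355. The protocol states neither extension. The gap between the columns shows how much depends on a rule that is not written down.

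**The case against.** The strongest reply on replacements is that the limit speaks of the first six subjects without saying whether they are the first six enrolled or the first six who count. Sections 3.2.1 and 4.1.2 order replacement at every level, and a replacement who could not count would serve little purpose. Section 3.2.1 also plans at least six in the 3+3 step at 1000 mg BID, which leaves room for one. On this view the limit only separates the 3+3 subjects from the 14 added later. That reading is reasonable, and it means the documents do not support saying that replacements are definitely shut out or that 1000 mg BID cannot complete its count. What stands is that no sentence says a replacement takes the vacated place, and that the limit comes before the evaluability test.

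On the other branch, a reader might infer that all 20 enter the set and that the MTD could then be overturned. Neither follows. Only subjects who are evaluable or have a DLT enter. Their membership also rests on their being counted as dose escalation subjects, which Section 3.2.1 implies by placement but does not state. They enrol at an MTD that has already been defined. Under Sections 3.2.1 and 3.2.3 the safety review team does this, reviewing each level after up to six subjects, and nothing provides for a re-test with the 20. The count-reading percentages alone would also overstate the effect: 2 of 26 is 7.7%, less than half of 1/6.

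Finally, SAP Section 1 says the study stopped during Phase 1b for lack of efficacy, so the other branch may never have arisen. The SAP still reports DLTs on this set, so the 1000 mg BID denominator matters wherever there are data at that level.

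**Conclusion.** The point holds as a defect in the definition of the analysis set, and it should be corrected. Between them, the protocol's 1000 mg BID limit, the unlimited 20 at the MTD and the SAP's missing limit allow fewer than 6, up to 20 or up to 26 subjects under a rule written for 6. The SAP's statement of no deviations does not fit the difference at 1000 mg BID.

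The consequence is confined to the reported DLT denominator and its consistency with the MTD definition. The real-time escalation decision on up to six subjects is largely unaffected. The shortfall at 1000 mg BID depends on the literal reading and on a non-evaluable rate that the documents do not give. The figure of 26 is a ceiling and depends on the 20 being treated as dose escalation subjects. The documents do not show how many subjects were treated at each level, so the effect on the actual report cannot be sized.

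**What to change.** Reconcile the protocol synopsis (Statistical Methods), protocol Section 8.3.1.4, and SAP Sections 3.1.4 and 7.1.7 on these points:

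- **MTD count.** At each dose level, use up to the first six DLT-evaluable subjects enrolled for the 3+3 decision, with replacements taking the place of non-evaluable subjects. The words up to are needed because Section 3.2.1 allows escalation after three subjects without a DLT.
- **Subjects added after a level is cleared.** Treat the 14 at 1000 mg BID and the 20 at the MTD alike, outside the 0-or-1-of-6 count.
- **Where their events go.** Summarise their events meeting DLT criteria in Days 1–21 separately by dose level, next to the main DLT table. They need their own label, because SAP 7.1.7 reserves DLT-type AE for events after Day 21.
- **SAP Section 7.7.** Record any remaining difference from the protocol.

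This settles the denominator only. Whether DLTs in the added subjects should prompt a fresh look at the MTD is a dose-finding question for the sponsor to state.

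The cost is a few sentences in four places, plus one separate summary. No extra subjects or data are needed. If the SAP is already final, its Section 1 provides for documenting the change in the study report.

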#### 8.3.1.5. Pharmacokinetics (PK) Analysis Set

The PK Analysis Set includes subjects in the Safety Analysis Set who have received the study drug and have at least 1 sample with detectable drug concentration.

CCI [REDACTED]

### 8.4. Data Handling Conventions

By-subject listings will be created for important variables from each eCRF module. Summary tables for continuous variables will contain the following statistics: N (number in analysis set), n (number with data), mean, standard deviation, 95% CIs on the mean, median, minimum, and maximum. Summary tables for categorical variables will include: N, n, percentage, and 95% CIs on the percentage. Unless otherwise indicated, 95% CIs for binary variables will be calculated using the binomial distribution (exact method) and will be 2-sided. Data will be described and summarized by cohort, analysis set, and time point.

The baseline value will be the last (most recent) pretreatment value before or on the first dosing date of study drug. As appropriate, changes from baseline to each subsequent time point will be described and summarized. Graphical techniques (eg, waterfall plots, Kaplan-Meier [KM] curves, line plots) may be used when such methods are appropriate and informative. Data from all sites will be pooled for all analyses. Analyses will be based upon the observed data unless methods for handling missing data are specified. If there is a significant degree of non-normality, analyses may be performed on log-transformed data or nonparametric tests may be applied, as appropriate.

### **8.5. Demographic Data and Baseline Characteristics**

Demographic and baseline measurements will be summarized by cohort, indication, and treatment using standard descriptive methods.

Demographic summaries will include sex, race/ethnicity, and age.

Baseline data will include summaries of body weight, height, ECOG performance status score, 12-lead ECG, and PD-L1 expression (TPS or CPS).

### **8.6. Efficacy Analysis**

In efficacy analysis, ORR will be evaluated by tumor type and treatment in FAS. Tumor types with less than 5 subjects enrolled will be pooled for ORR summary. Subjects who do not have sufficient baseline or on-study tumor assessment to characterize response will be counted as nonresponders. Estimates and the corresponding 95% CIs based on the Clopper-Pearson exact method will be provided. The potential impact of subject baseline characteristics on treatment response may be explored with logistic regression modeling.

Medians, first quartile (Q1), third quartile (Q3) of the PFS distribution, and the proportion of subjects who are progression-free at Weeks 12, 24, and 48 from the first dosing date will be estimated by tumor type using the KM method along with the corresponding 95% CIs. KM curves will be provided.

The similar ORR and PFS analyses will be conducted using the investigator assessments and independent review committee (IRC) assessments if available.

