**Criteria for Evaluation:**

- Safety:** Safety will be evaluated by assessment of clinical laboratory tests, physical examination, 12-lead ECG, vital signs measurements, and the documentation of AEs. AEs will be graded using NCI-CTCAE version 5.0.
- Efficacy:** Efficacy will be evaluated by overall response rate (ORR) (CR + PR), assessed as per RECIST v 1.1 with modifications, or per Lugano 2014 response criteria for cHL, and progression-free survival (PFS), defined as the interval from the first dosing date of study drug to the earlier of the first documentation of definitive disease progression or death from any cause.
- Pharmacokinetics:** The following PK parameters for GS-4224 will be calculated as applicable:  $T_{last}$ ,  $T_{max}$ ,  $C_{max}$ ,  $C_{trough}$ ,  $AUC_{last}$ ,  $AUC_{tau}$ , and  $t_{1/2}$ . Dose proportionality and time-dependency in drug exposure may be evaluated as applicable.

CCI

[REDACTED]

---

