#### 4.2. Inclusion Criteria

Subjects must meet all of the following inclusion criteria to be eligible for participation in this study. Additional indication-specific inclusion criteria for 1000 mg BID Dose Escalation Cohort and Phase 2 are provided in [Appendix 3](#).

- 1) Male or female  $\geq 18$  years of age
- 2) Dose Escalation Cohorts: Histologically or cytologically confirmed advanced malignant solid tumor that is refractory to or intolerant of all standard therapy or for which no standard therapy is available.
- 3) Dose Expansion and 1000 mg BID Dose Escalation Cohorts: Subjects must have available sufficient and adequate formalin-fixed tumor sample preferably from a biopsy of a tumor lesion obtained either at the time of or after the diagnosis of advanced disease has been made and from a site not previously irradiated. Alternatively, subjects must agree to have a biopsy taken prior to entering the study to provide adequate tissue. For the 1000 mg BID dose escalation cohort, subjects with melanoma, Merkel cell, MSI-H cancers, and cHL are not required to have archival or fresh biopsy tissue.

CCI

- 5) All persisting toxic effects of any prior antitumor therapy resolved to National Cancer Institute-Common Terminology Criteria for Adverse Events (NCI-CTCAE) version 5.0 Grade  $\leq 1$  or baseline before the first dose of study drug (with the exception of alopecia [Grade 1 or 2 permitted] and neurotoxicity [Grade 1 or 2 permitted]).
- 6) Eastern Cooperative Oncology Group (ECOG) Performance Status of  $\leq 2$
- 7) Life expectancy of  $\geq 3$  months, in the opinion of the investigator
- 8) Adequate organ function defined as follows:
  - a) Hematologic: Platelets  $\geq 100 \times 10^9/L$  ( $\geq 60 \times 10^9/L$  in subjects with HCC); Hemoglobin  $\geq 9.0$  g/dL; ANC  $\geq 1.5 \times 10^9/L$  (without blood transfusion, platelet transfusion, or growth factors within previous 7 days of the hematologic laboratory values obtained at screening visit)
  - b) Hepatic: AST/ALT  $\leq 2.5 \times$  upper limit of normal (ULN) (if liver metastases are present,  $\leq 5 \times$  ULN); total or conjugated bilirubin  $\leq 1.5 \times$  ULN
  - c) Renal: Creatinine clearance ( $CL_{cr}$ )  $\geq 45$  mL/min as calculated by the Cockcroft-Gault method

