### **Tumor response evaluation**

#### **Evaluation of target lesions**

**Complete Response (CR):** Disappearance of all target lesions. Any pathological lymph nodes (whether target or non-target) must have reduction in short axis to <10mm.

**Partial Response (PR):** At least a 30% decrease in the sum of diameters of target lesions, taking as reference the baseline sum diameters.

**Progressive Disease (PD):** At least a 20% increase in the sum of diameters of target lesions, taking as reference the smallest sum on study (this includes the baseline sum if that is the smallest on study). In addition to the relative increase of 20%, the sum must also demonstrate an absolute increase of at least 5 mm. (Note: the appearance of one or more new lesions is also considered progression).

**Stable Disease (SD):** Neither sufficient shrinkage to qualify for PR nor sufficient increase to qualify for PD, taking as reference the smallest sum diameters while on study.

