**Table 2 – Time point response: patients with non-target disease only.**

Non-target lesions	New lesions	Overall response
CR	No	CR
Non-CR/non-PD	No	Non-CR/non-PD a
Not all evaluated	No	NE
Unequivocal PD	Yes or No	PD
Any	Yes	PD

CR = complete response, PD = progressive disease, and NE = inevaluable.  
 a 'Non-CR/non-PD' is preferred over 'stable disease' for non-target disease since SD is increasingly used as endpoint for assessment of efficacy in some trials so to assign this category when no lesions can be measured is not advised.

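### No visible entry criterion requires measurable disease, so solid-tumor subjects who can never score a PR stay in the ORR denominator and may dilute ORR by an unreported amount

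*Protocol*

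**What the plan says.** Protocol 8.6 sets the analysis: "In efficacy analysis, ORR will be evaluated by tumor type and treatment in FAS". Protocol 8.3.1.2 fixes the denominator: "The Full Analysis Set (FAS) includes all subjects who took at least 1 dose of study treatment". SAP 3.1.2 defines the set the same way. The synopsis (Criteria for Evaluation) defines ORR as CR plus PR, by RECIST v1.1 with modifications, or by Lugano 2014 for cHL. For subjects whose response cannot be determined, 8.6 adds: "Subjects who do not have sufficient baseline or on-study tumor assessment to characterize response will be counted as nonresponders". Precision is given by an interval only: "Estimates and the corresponding 95% CIs based on the Clopper-Pearson exact method will be provided".

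Eligibility is in Protocol 4.2 ("Subjects must meet all of the following inclusion criteria to be eligible for participation in this study") and in the tumor-specific lists of Appendix 3. All 16 general criteria can be read in the synopsis. That includes criterion 4, which is blacked out in 4.2 and concerns PD-L1 expression. Neither list mentions a measurable lesion.

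Appendix 6 defines PR through target lesions alone: "At least a 30% decrease in the sum of diameters of target lesions, taking as reference the baseline sum diameters". Its Table 2 ("Time point response: patients with non-target disease only") provides for subjects with no target lesion. The possible outcomes there are CR, non-CR/non-PD, NE and PD.

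**The concern.** A solid-tumor subject with only non-target disease can enter any cohort, be fully imaged and show real tumor shrinkage, and still not count as a responder unless all disease disappears. That subject remains in the FAS. ORR then reflects case mix as well as drug activity.

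This matters most where response is of interest. Protocol 3.2.2 gives preliminary efficacy as a purpose of Cohort B1. The 1000 mg BID cohort is likewise restricted to checkpoint-naive subjects and, for most tumor types, selected on PD-L1. ORR is reported by tumor type, with types of fewer than 5 subjects pooled, so one or two such subjects can move an estimate. The baseline summaries listed in Protocol 8.5 and SAP 5.2 do not count subjects with and without measurable disease, so a reader of those tables could not judge the effect.

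**Working it through.** **Inputs from the documents.** Up to 20 subjects in the 1000 mg BID cohort (Protocol 3.2.1); about 40 in Cohort B1 (3.2.2); FAS denominator (8.3.1.2, 8.6); PR definition and Table 2 (Appendix 6).

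**Inputs assumed, because the documents give none.** p = response rate in measurable disease; m = share of subjects with non-target disease only; c = CR rate in that share.

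**1. The plan's own figures.** There is no null ORR, target ORR or power calculation to reproduce. Enrollment adds up: 4 QD levels × 6 + 20 at 1000 mg BID = 44, and 44 + 36 (biopsy substudy, SAP 1.3) + 40 (Cohort B1) = 120, as stated.

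**2. Is measurable disease required anywhere?** Not in the 16 general criteria and not in Appendix 3. Lesions are measured at baseline (synopsis, Screening) and scans are used to find target lesions (6.6.1), but these are procedures and not entry conditions. Entry also does not shut out disease that Appendix 6 calls non-measurable. Exclusion 11, for example, admits subjects who are stable after treatment for an effusion or ascites.

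**3. Dilution.** Expected FAS ORR = (1 − m)p + mc. The loss relative to p is m(p − c), which is positive whenever c < p.

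**4. Chance of no responder among 20, with c = 0.** P(0) = [1 − (1 − m)p]^20. For p = 20%: 0.80^20, 0.82^20, 0.84^20, 0.86^20. For p = 15%: 0.85^20, 0.865^20, 0.88^20, 0.895^20.

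| m | FAS ORR, p = 20%, c = 0 | FAS ORR, p = 20%, c = 5% | P(0 of 20), p = 20% | P(0 of 20), p = 15% |
|---|---|---|---|---|
| 0 | 20% | 20% | 1.2% | 3.9% |
| 10% | 18% | 18.5% | 1.9% | 5.5% |
| 20% | 16% | 17% | 3.1% | 7.8% |
| 30% | 14% | 15.5% | 4.9% | 10.9% |

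If exactly 2, 4 or 6 of the 20 lack target lesions, instead of each subject having chance m, the p = 20% figures are 0.80^18 = 1.8%, 0.80^16 = 2.8% and 0.80^14 = 4.4%.

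**5. What a supplementary denominator would show (Clopper-Pearson 95% intervals).** Suppose 8 responders in Cohort B1:
- all 40 subjects: 20.0% (9.1 to 35.7)
- 36 subjects (10% without target lesions): 22.2% (10.1 to 39.2)
- 32 subjects (20% without): 25.0% (11.5 to 43.4)

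With no responders the estimate is 0% whatever the denominator. Only the upper limit moves: 16.8% for 0/20, 18.5% for 0/18, 20.6% for 0/16.

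**6. Small tumor types.** In a type with 5 subjects, one without a target lesion is a fifth of the denominator: one responder is 1/5 = 20% in the FAS and 1/4 = 25% among those with target lesions.

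**The case against.** The strongest reply has five parts.

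- **The nonresponder sentence is not a defect.** It is a standard conservative rule for missing assessments. A fully imaged subject with non-target disease is classified by Table 2, where CR is available and counts. This stands: the gap comes from eligibility combined with the FAS denominator.
- **ORR among all dosed subjects is a legitimate quantity.** It is what the plan says it will report. This stands too, so the right word is dilution relative to ORR in measurable disease. It does not answer the reader who wants to know how many subjects could have shown a PR.
- **The share may be near zero.** The two cohorts enroll locally advanced, inoperable or metastatic disease, in which measurable lesions may be usual. The 10% to 30% range has no support in the documents. This limits the size of the point, and it is also a reason to report the count.
- **cHL does not fit the argument.** Under Appendix 7 a partial metabolic response can be scored with residual masses of any size. A measurability rule for cHL could exclude potential responders. This stands, and the fix leaves cHL alone.
- **It is late.** SAP section 1 says that Phase 2 was not started and that only Phase 1b will be reported, in a synoptic report. This limits the use of an eligibility change but not of the supplementary analysis.

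A reader might go further and infer that the design made a negative result easier to reach, or that dilution contributed to stopping the study, since SAP section 1 attributes the stop to absence of objective efficacy in Phase 1b. The documents support neither. They set no null ORR, success threshold or futility rule. SAP 3.5 plans no formal testing, and the primary endpoint is DLT incidence. SAP section 1 gives no ORR, denominator or decision rule, and nothing shows that any enrolled subject lacked a target lesion.

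**Conclusion.** The point holds as a gap in eligibility and reporting. For solid tumors assessed by RECIST, the FAS ORR falls below ORR in measurable disease by m(p − c) whenever subjects with non-target disease only are enrolled and their CR rate is below p. Under the assumed shares of 10% to 30%, with p = 20%, that is 2 to 6 percentage points if none of them reaches CR, and 1.5 to 4.5 points if 5% do. A zero count among 20 becomes somewhat more likely but stays below 5% at p = 20%; at p = 15% it reaches 10.9%.

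The direction follows from the definitions. The size rests on m, p and c, none of which the documents give, and it is nil if every subject had a target lesion. Two limits remain: the SAP text passes from section 5 to section 7, so any efficacy section could not be checked, and some objectives and endpoints are blacked out.

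**What to change.** **Analysis (Protocol 8.6, and the SAP).** Keep the FAS ORR. Report, by cohort and tumor type, how many RECIST subjects had no target lesion at baseline. Add a supplementary ORR, with its Clopper-Pearson interval, in FAS subjects with at least one baseline target lesion. Leave cHL under Lugano with no measurability restriction. SAP 3.4 names no subgroups, so the addition must be written in; after SAP finalization, SAP section 1 requires that it be documented in the study report.

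**Eligibility (Protocol 4.2 and synopsis).** For solid tumors in the 1000 mg BID cohort and Cohort B1, require at least one measurable lesion at baseline as defined in Appendix 6. This matters only for further enrollment or reuse of the protocol.

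**Cost.** A few more screen failures if enrollment continues, and a few extra rows in each ORR table, because ORR is broken down by tumor type and treatment. No new procedure is needed: Appendix 6 already sorts baseline lesions into measurable and non-measurable.
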